5.4 STRATEGIES FOR RECRUITMENT AND RETENTION

Recruitment:

The study team will obtain a limited waiver of HIPAA authorization to allow pre-screening for patient eligibility. The team will consult at least weekly with the Minimum Data Set Nurse, social worker, or other personnel involved in coordinating clinical care for newly admitted patients in each SNF by phone, email, or in-person to identify patients that are expected to be discharged from the SNF to home, and subsequently screen the medical records of all patients expected to discharge from the SNF to home.

After identifying potentially eligible patients, the study team will recruit SNF patients and their caregivers in-person (or, when risk mitigation related to COVID-19 prevents in-person contact, we will recruit virtually, using an iPad and connection via ZOOM) within 10 days of their admission and will review the patient's medical record to confirm eligibility. For patients with cognitive impairment, the team will recruit the patient's legally authorized representative to respond to survey questions as the patient's proxy.

Recruitment will be conducted in the SNFs through in-person interactions (or, when risk mitigation related to COVID-19 prevents in-person contact, we will recruit virtually, using an iPad and connection via ZOOM). If necessary, recruitment can also be conducted by telephone for caregivers. All participants will provide written informed consent (or, when risk mitigation related to COVID-19 prevents in-person contact, we will obtain consent verbally using an iPad and connection via ZOOM) for study participation. When written consent is not feasible, we will obtain witnessed verbal consent with the assistance of nursing home personnel via the iPad and Zoom connection). Legally authorized representatives will give consent for patients with cognitive impairment. Consent and HIPAA Authorization could also be obtained verbally in the situation that a participant is unable to physically sign these documents.

Retention:

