- In Step 1, SNF nurses, rehabilitation therapists, and social workers will develop a Transition Plan of Care and prepare the patient and caregiver to manage the patient's serious illness and functional needs at home. Staff also will use American Geriatrics Society recommendations for self-care at home in the context of the COVID-19 pandemic (when applicable).

- In Step 2, the Connect-Home Activation RN (employed in the collaborating home health agency) will visit the patient and caregiver at home within 24 hours of discharge; the nurse will work with them to activate the Transition Plan of Care at home. Nurses also will use American geriatrics Society recommendations for self-care at home in the context of the COVID-19 pandemic (when applicable).

Process	Patient/Caregiver Services and Supports	Day
Step 1. Transitional care in the SNF ²⁷	
Set goals for home-based care (45 minutes)
 
Consulting with the patient/caregiver, SNF staff use the EHR template to describe goals in the patient’s Transition Plan of Care, targeting 6 key care needs (home safety and level of assistance, advance care planning, symptom management, medication reconciliation, function and activity and coordination of follow-up medical care). Staff will use American Geriatrics Society recommendations for self-care at home in the context of the COVID-19 pandemic (when applicable).
 
 • Nurses create goals for planned treatments at home, and responses to emerging symptoms or other health changes at home • Rehabilitation therapists create goals for mobility, transfers and self-care at home. • Social worker creates goals for caregiver support, follow-up care & discharge disposition. 	2 - 17

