This measure will be assessed at 30 and 60 days post discharge, through telephone interview with the patient (or with the patient's legally authorized representative, responding to survey questions as the patient's proxy in cases of patients with cognitive impairment).

Emergency Department Use

This assessment is self-reported by the patient; it is a count of emergency department visits without a hospital stay after SNF discharge.

This measure will be assessed at 30 and 60 days post discharge, through telephone interview with the patient (or with the patient's legally authorized representative, responding to survey questions as the patient's proxy in cases of patients with cognitive impairment).

Death Report by Caregiver

This assessment is self-reported by the caregiver regarding patient death after SNF discharge.

This measure will be assessed at 30 and 60 days post discharge, through telephone interview with the caregiver.

Co-variate assessments will be collected in-person and from the medical record. For some caregivers, co-variate data can be collected by phone. Co-variate data are as follows:

- Patient Data collected in person:
 - Study of Osteopathic Fractures Index ¹⁰⁹, measuring frailty of the patient
 - ENRICH Social Support Inventory ¹¹⁰, measuring social support of the patient
- Patient data collected with SNF chart abstraction:
 - Demographics
 - Health insurance status
 - Medical Information
 - Depression (Minimum Data Set section D) ⁹⁴
 - Function (Minimum Data Set section GG) ⁹⁴
 - Cognitive status (Minimum Data Set section C) ^{94, 111}
 - SNF care (i.e., SNF length of stay, urgent or acute treatment while in the SNF)
 - Discharge destination
 - Charlson Comorbidity Index scores ¹¹² (calculated using the problem list in the medical record)
 - Yes or No that the SNF admission date was before the mandated pause in research activities (related to the COVID-19 pandemic)
 - History of COVID-19 diagnosis and treatment in the index hospitalization and/or in the SNF
- Caregiver data collected in-person or by phone:
 - Demographics
 - Relationship to patient
 - Employment
 - Count of days per week providing patient care
 - History of COVID-19 diagnosis and treatment

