9.3 POPULATIONS FOR ANALYSES

An intent to treat analysis will be used in which all patients/caregivers are included in the analysis according to their treatment allocation at enrollment, regardless of whether they receive the full intervention.

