9.4 STATISTICAL ANALYSES

9.4.1 GENERAL APPROACH

Descriptive statistics will be used for all variables. If patients or caregivers with missing covariates are few (< 5%), unconditional mean imputations will be used to impute missing values for continuous covariates and unconditional mode imputation for categorical covariates. If 5%-15% of patients or caregivers have missing covariates, conditional mean imputation will be used. If missing covariate data exceed 15%, multiple imputation will be used. Missing outcomes will not be imputed. For continuous variables that are highly skewed, the statistical team will log-transform the data for analysis. All statistical tests will be two-tailed with 0.05 significance levels. Also, descriptive statistics will be used to describe intervention fidelity (receipt, delivery and enactment). Finally, in the absence of strong temporal effects, balance in covariates is expected between control and intervention patients; supplemental analyses will involve assessing the impact of the covariates (i.e., insurance provider, SNF length of stay, race, gender, and others determined with bivariate analyses) on outcomes in the statistical models for aims 1-3.

Finally, to determine the extent the intervention effect can be attributed to home health care use, a general multilevel approach will be used to causal mediation analysis to evaluate home health care use as a mediator for intervention effect on outcomes as a secondary analysis. This approach uses two

random effects models within the counterfactual framework: 1) for the mediator (number of days of home health care use) as a function of treatment condition and covariates and 2) for the outcome as a function of treatment condition, mediator, and covariates. Outputs include indirect and direct effects of the intervention.

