9.4.2 ANALYSIS OF THE PRIMARY EFFICACY ENDPOINT(S)

In the models for patient preparedness for discharge (CTM-15 score), data will be included that was provided by the patient or by caregiver (for patients that are not able to answer survey questions). We will use hierarchical linear models (HLM) to compare observations between intervention and usual care periods for CTM-15 score at seven days post-discharge. Linear mixed models or HLM allow for different numbers of patients per site, while accounting for correlated responses between patients within the same SNF. Let Y_{ijk} denote the CTM-15 score for patient k in SNF i and period (enrollment month) j ; ($i = 1, 6$; $j = 1, \dots, 22$). The basic HLM is, where μ is an intercept term, γ_i is a random effect for SNF, accounts for a potential linear temporal trend, δ_j is a random effect for period j nested within SNF i , T_i is an indicator for the treatment condition (i.e., 1 if Connect-Home; 0 is standard discharge procedures), θ is the treatment effect, and ϵ_{ijk} is an error term. Furthermore, we assume a variance components structure such that all random effects are independent with, and where subscripts “c”, “p” and “e” denote cluster (i.e., SNF), period and error variance components, respectively. The correlation structure induced by these random effects allows the within-SNF correlation of outcomes from two patients enrolled in the same month (ICC_W) to be different from the within-SNF correlation of outcomes from patients enrolled in different months (ICC_B). Specifically, by denoting the total variance, the intraclass correlations are $ICC_W = \frac{\sigma_c^2 + \sigma_p^2}{\sigma_c^2 + \sigma_p^2 + \sigma_e^2}$, and $ICC_B = \frac{\sigma_c^2}{\sigma_c^2 + \sigma_p^2 + \sigma_e^2}$. For CTM-15, the basic HLM model will be amended by including additional explanatory variables as fixed effects: CTM-15 score source (patient or caregiver), patient age, gender and race. Due to skewness of the CTM-15 score distribution found in our preliminary data, we expect this outcome will be log-transformed prior to analysis. The group difference in log CTM-15 scores (intervention vs. control) across the study periods will be estimated along with a 95% confidence interval. A sensitivity analysis will be conducted to assess whether the effect of Connect-Home depends on the number of months that an SNF has been operating under the Connect-Home protocol. This is achieved by extending the HLM so that separate effects of Connect-Home are estimated when the Connect-Home protocol has been implemented for ≤ 3 months versus > 3 months in order to examine whether the impact of Connect-Home is sustained three months following its initial implementation in the staff training period. A similar linear mixed model will be applied for the Preparedness for Caregiving outcome, except that respondent source is not included.

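### The supplemental models adjust for SNF length of stay, which is completed only at discharge and during Step 1, so their adjusted effect may be distorted

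*Combined protocol and SAP*

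**What the plan says.** Section 9.4.1 states that "in the absence of strong temporal effects, balance in covariates is expected between control and intervention patients", and continues that "supplemental analyses will involve assessing the impact of the covariates" in the models for aims 1-3. The covariates are "insurance provider, SNF length of stay, race, gender, and others determined with bivariate analyses". It gives no candidate list or threshold, and does not say whether screening is against outcome or treatment. The same section plans a mediation analysis of home health care use, whose covariates are not named.

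The timing is set elsewhere:

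- Section 5.4: recruitment takes place "within 10 days of their admission".
- Section 9.3: participants are analyzed "according to their treatment allocation at enrollment".
- Section 6.1.1, Table 1: Step 1 opens with "Set goals for home-based care (45 minutes" minutes' worth of goal setting on days 2-17. Preparation follows on days 6-20, with hand-off in the last one to two days before discharge. Step 2, at home, is on day 21.
- Section 1.2: SNF chart abstraction sits in the 7-day post-discharge column.

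Section 8.1 nevertheless lists "SNF care (i.e., SNF length of stay, urgent or acute treatment while in the SNF" as covariate data, and Section 9.4.4 repeats the item under baseline statistics, together with discharge destination.

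The primary CTM-15 model in Section 9.4.2 has its own fixed set: "CTM-15 score source (patient or caregiver), patient age, gender and race".

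**The concern.** A covariate used to adjust a treatment effect should be settled before treatment can influence it. Length of stay is not. Connect-Home adds goal setting, a planning meeting and 2.5 hours of preparation before discharge, so an effect on the discharge date is possible.

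If there is one, adjustment can go wrong in two ways. Where stay itself influences preparedness, adjusting removes that part of the effect. Where stay and outcome share an unmeasured cause such as severity of illness, adjusting opens a path between treatment and that cause.

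What is at stake is the reading of a supporting analysis. In a stepped wedge, condition is tied to calendar time, and Section 9.4.1 expects covariate balance only without strong temporal effects. A reader will therefore look to the supplemental models to see whether imbalance explains the result. With a covariate in them that treatment may have changed, a difference from the primary estimate could reflect either corrected imbalance or the adjustment itself.

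**Working it through.** **1. The plan's own figures (Section 9.2).** 360 x (1 - 0.23) = 277.2, which matches the stated 277. exp(0.15) = 1.162, which matches the stated 16% increase. The 89% power cannot be checked directly, because no SD of log CTM-15 is given. Using the Figure 2 layout, ICCs of 0.10 and 0.05, a linear time trend and two-sided 5%, an SD of about 0.194 returns 89%, with a standard error of about 0.047. As read from the text, Figure 2 has 92 SNF-months (368 patients at 4 each, against 360). A 90-cell version gives the same SD.

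**2. Timing.** Assume the days in Table 1 count from admission. With enrollment no later than day 10 and discharge at about day 20, at least (20 - 10)/20 = 50% of the planned stay accrues after enrollment.

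**3. Formula.** In a linear model,

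adjusted effect = total effect - a x k x SD,

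where a is the change in stay caused by Connect-Home (in SDs of stay) and k is the coefficient of stay given treatment (in outcome SDs per SD of stay, including any shared cause). The documents give neither, so both are assumptions.

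**4. Numbers.** Total effect 0.15, SD 0.194, |k| = 0.3:

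| Change in stay, a | Shift = a x 0.3 x 0.194 | Adjusted effect | Share of 0.15 |
|---|---|---|---|
| 0 | 0 | 0.150 | 0% |
| ±0.10 | 0.006 | 0.144 to 0.156 | 4% |
| ±0.25 | 0.015 | 0.135 to 0.165 | 10% |
| ±0.50 | 0.029 | 0.121 to 0.179 | 19% |

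Smaller |k| shrinks these in proportion; |k| = 0.1 with |a| = 0.10 gives about 1%. The sign follows the signs of a and k. The largest shift, 0.029, is about 0.6 of the standard error (0.029/0.047). The shift also scales with the SD: in the |a| = 0.50 row, an SD of 0.15 gives 0.0225 (15%) and 0.25 gives 0.0375 (25%), although those SDs correspond to 98.5% and 70% power rather than 89%.

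**5. Simulation check.** 1,000 stepped-wedge trials of 277 patients per scenario, in outcome SD units, true effect 0.4, variance components treated as known:

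- a = 0: 0.417 and 0.418 with and without stay, so no shift.
- a = 0.25, k = -0.2: 0.385 unadjusted, 0.433 adjusted. The formula predicts +0.05; observed +0.048.
- a = 0.50, k = -0.2: 0.393 unadjusted, 0.492 adjusted. Predicted +0.10; observed +0.099.
- a = 0.25, k = 0.2: 0.395 unadjusted, 0.346 adjusted. Predicted -0.05; observed -0.049.

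**6. Screening.** Choosing among 10 pre-enrollment candidates at p < 0.05 moved the mean estimate by at most 0.004, against a Monte Carlo standard error of about 0.008. Rejection under the null was 6.3-6.4% with screening and 7.1% without.

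**The case against.** The best reply is that measured after enrollment does not mean changed by treatment. Length of stay is not an objective, endpoint or hypothesis in Sections 3 and 9.1, and nothing in the documents says that Connect-Home alters it. This stands: the distortion is conditional, and a reader who infers that the adjusted effect is biased goes further than the documents allow.

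Three other stronger readings also fail.

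- That the screening itself biases the effect: the simulation did not show this for pre-enrollment candidates. What remains is that the rule is not prespecified and could bring in post-enrollment items from Section 9.4.4, such as urgent or acute treatment in the SNF.
- That discharge destination is an equal problem: under Section 7.2, patients who do not go home are not analyzed, so it will hardly vary.
- That the mediation models adjust for stay: Section 9.4.1 does not name their covariates. The point there is precautionary. If stay were included and treatment changed it, stay would be a treatment-induced confounder of mediator and outcome, and standard direct and indirect effects would not be identified.

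It can also be argued that stay may drift over calendar time for reasons unrelated to treatment, for instance around the COVID-19 pause, and is therefore worth examining. It is, but the model cannot tell such drift from an effect of Connect-Home on stay. Tabulating stay by condition shows the difference without presenting an adjusted effect that depends on its cause.

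**Conclusion.** The point holds as a conditional weakness in a supporting analysis. Section 9.4.1 names a covariate that is completed after enrollment and during delivery of the intervention, while Section 9.4.4 classes it as baseline. The supplemental effect is distorted if two things are true: Connect-Home changes length of stay, and stay is associated with the outcome given treatment. The documents settle neither. For changes of 0.10 to 0.50 SD with an association of 0.3 SD, the shift is about 4% to 19% of 0.15, in either direction; with no change in stay it is zero. These figures rest on assumed a and k and on an SD inferred from the stated power.

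A reader might infer that the primary result is compromised. It is not: the CTM-15 model in Section 9.4.2 uses a fixed set without length of stay, and its estimate and power are unaffected.

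**What to change.** In Section 9.4.1:

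- Remove SNF length of stay from the supplemental adjustment set. State that neither it nor urgent or acute SNF treatment may enter through the screened additions or as a mediation covariate.
- Replace the bivariate screening with a fixed list of pre-enrollment covariates: insurance, race, gender, frailty, Charlson score, index hospital stay, function and cognition, and days from SNF admission to enrollment.
- Specify that function and cognition are the values at or before enrollment, because charts are abstracted after discharge. Section 5.1 already uses both at eligibility.
- Report length of stay by condition, descriptively or as a post-enrollment outcome, and move it out of the baseline list in Section 9.4.4.

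The cost is wording. Every replacement variable is collected or derivable. The only loss is that a model containing length of stay is no longer presented as an adjusted treatment effect.

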2.5 To assess caregiver distress 30 and 60 days after discharge from a skilled nursing facility.	2.5 The Distress Thermometer, assessed 30- and 60-days post discharge. ²⁸	2.5 The Distress Thermometers includes 1 item on an 11-point scale, measuring negative affect related to caregiving for a severely ill person. Score ranges 0-10, with scores >4 associated with poor coping and depression.
Tertiary/Exploratory		
E.1 To assess the number of patients falls with injury 30 and 60 days after discharge from a skilled nursing facility.	E.1 Patient assessment of number of falls with injury, assessed 30- and 60-days post discharge. Falls are defined as an "unintentional change in position resulting in a resident coming to rest on the ground or lower level." ⁴³	E.1 Prior exploratory studies suggest that falls are a frequent event in the immediate post-discharge period. The count of falls in this study will be among the first to describe the impact of a transitional care

OBJECTIVES	ENDPOINTS	JUSTIFICATION FOR ENDPOINTS
E.2 To assess patient enrollment in hospice 30 and 60 days after discharge from a skilled nursing facility.	E.2 Patient assessment of enrollment in hospice, assessed 30- and 60-days post discharge.	intervention on the falls rate in the post discharge period. E.2 No prior transitional care study reports the rate of hospice enrollment after SNF-home transfers. Data collected with this item will suggest hospice use in a severely ill sample of SNF patients.
E.3 To assess the patient's number of days in home health care 30 and 60 days after discharge from a skilled nursing facility.	E.3 Nurse and rehabilitation therapist assessment of number of days in home health care, assessed 30- and 60-days post discharge.	E.3 Data collected with this measure will indicate the intensity of home care services in the post discharge period. These data will support a secondary analysis to determine the degree that outcomes of the Connect-Home intervention are mediated by the intensity of home health care use.

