8 STUDY ASSESSMENTS AND PROCEDURES

8.1 EFFICACY ASSESSMENTS

The procedures and assessments described in this section will be performed at the time point(s) described in the schedule of activities schedule in section 1.3.

All variables will be measured with chart reviews and/or interview-questionnaires with patients and caregivers. Data collection will be identical for intervention and control periods.

Care Transitions Measure-15 (CTM-15)³³

Self-reported preparedness for discharge will be assessed using the CTM-15. It includes 15 questions on a 4-point scale, with a summary score ranging from 0-100. Higher scores are associated with less acute care use after discharge.

This measure will be assessed at 7 days post-discharge, through telephone interview with the patient (or with the patient's legally authorized representative, responding to survey questions as the patient's proxy in cases of patients with cognitive impairment).

Preparedness for Caregiving Scale (PCS)³⁵

Self-reported preparedness for caregiving will be assessed using the PCS. It includes 8 questions on a 5-point Likert scale (0-4), with a range of 0-32. Higher scores are associated with less anxiety.

This measure will be assessed at 7 days post-discharge, through telephone interview with the caregiver.

McGill Quality of Life Questionnaire - Revised (MQoL-R)³⁷

Quality of life across disease trajectories is measured using the MQoL-R. It includes 16 items on a 0-10 point Likert scale.

This measure will be assessed at 30 and 60 days post discharge, through telephone interview with the patient (or with the patient's legally authorized representative, responding to survey questions as the patient's proxy in cases of patients with cognitive impairment).

Life Space Assessment³⁸

Patient function is measured using the Life Space Assessment. It includes 5 Likert scales that correspond to a hierarchy of levels of mobility (each scored 0-4). Weights are the product of the "Life-space Level" (range 1-5) and the "independence" score (range 1-2). Score ranges from 1-120, and lower scores are associated with falls and hospitalization.

This measure will be assessed at 30 and 60 days post discharge, through telephone interview with the patient (or with the patient's legally authorized representative, responding to survey questions as the patient's proxy in cases of patients with cognitive impairment).

Zarit Caregiver Burden Scale^{41,42}

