9.4.4 BASELINE DESCRIPTIVE STATISTICS

Co-variate data will be collected about patients in person and from the medical record. Data about caregivers will be collected in person or by phone.

Patient data collected in person:

- Frailty (Study of Osteopathic Fractures Index)⁴⁷
- Social support (ENRICH Social Support Inventory)⁴⁸

Patient data collected with SNF chart abstraction:

- Demographics
- Health insurance status (Medicare Advantage/Medicare fee-for-service/Medicaid/private)

- Living arrangements before index hospitalization
- Medical history (primary diagnosis in the hospital discharge summary, hospital care (critical care, surgery and length of stay)
- Depression (Minimum Data Set section D)⁴⁹
- Function (Minimum Data Set section GG)⁴⁹
- Cognitive status (Minimum Data Set section C)⁴⁹
- SNF care (i.e., SNF length of stay, urgent or acute treatment while in the SNF)⁴⁹
- Discharge destination

Using the problem list in the medical record, the Charlson Comorbidity Index scores will be calculated for each patient.⁵⁰

Patient data collected with Home Health Care chart abstraction:

- Number of days of home health care use in 30 and 60 days after SNF discharge⁴⁰

Caregiver data collected in person or by phone:

- Demographics
- Relationship to patient
- Living arrangements
- Employment
- Count of days per week providing patient care.

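### The home health counts over 30 and 60 days lack the time order to mediate the day-7 outcomes, and they share their window with acute-care days and falls

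*Combined protocol and SAP*

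**What the plan says.** Section 9.4.1 sets out a causal mediation analysis, classed as secondary, to "evaluate home health care use as a mediator for intervention effect on outcomes". It fits one random effects model "for the mediator (number of days of home health care use) as a function of treatment condition and covariates" and a second for the outcome given treatment, mediator and covariates. "Outputs include indirect and direct effects of the intervention". The section gives no list of outcomes, no time points and no counting window for the mediator.

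The window appears elsewhere. Section 9.4.4 lists the abstracted item as "Number of days of home health care use in 30 and 60 days after SNF discharge". Endpoint E.3 in section 3 uses the same two windows and says that the data will support an analysis of "the degree that outcomes of the Connect-Home intervention are mediated by the intensity of home health care use".

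The outcomes have these timings:
- **CTM-15 and PCS (primary):** day 7. For PCS, section 8.1 says: "This measure will be assessed at 7 days post-discharge, through telephone interview with the caregiver". Section 1.2 allows the patient call from 3 days before to 10 days after day 7, and the caregiver call within 2 days either side.
- **MQoL-R, Life Space Assessment, Zarit scale, Distress Thermometer:** days 30 and 60, each within 7 days either side.
- **Acute-care days and falls:** totals from discharge to day 30 and to day 60 (sections 1.1 and 9.4.3).

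Section 7.2 withdraws a patient who is hospitalised or re-admitted to a SNF after going home, and keeps the data collected before that event.

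**The concern.** A mediator has to act before the outcome that it is meant to explain. Home health days that accrue after a day-7 interview cannot have changed the answers given in it. If patients or caregivers who feel less prepared go on to use more home health care, the association runs from outcome to count, and the analysis would report it as an indirect effect. The direct effect would be off by the same amount.

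For acute-care days and falls, mediator and outcome build up side by side. An acute event can change later home health use, and a hospital stay can displace home health days. A model with one total for each cannot tell this from home health care preventing the event.

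At stake is the trial's statement of how much of the Connect-Home effect is due to home health care. The estimate of the effect itself is not at stake.

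**Working it through.** The plan states no figure on this point, so there is none to reproduce. The check compares windows, then uses two illustrations to show direction.

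**1. Day-7 outcomes.** Share of the count falling after the call = (W − d)/W, with W = 30 or 60 and d = day of the call.
- Call on day 7: (30 − 7)/30 = 77%; (60 − 7)/60 = 88%.
- Patient window, day 4 to day 17: 26/30 = 87% down to 13/30 = 43%; for the 60-day count, 56/60 = 93% down to 43/60 = 72%.
- Caregiver window, day 5 to day 9: 25/30 = 83% down to 21/30 = 70%; for the 60-day count, 55/60 = 92% down to 51/60 = 85%.

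**2. What that can do.** A simulation with a true indirect effect of zero assumed 276 patients, a treatment effect of 0.4 SD on a day-7 score, 3 home health days a week, and later use that depends on the score. It used ordinary least squares, the product of coefficients, and no clustering. For log-odds slopes of 0, −0.1, −0.2 and −0.3 per SD, the 30-day count gave false indirect effects of 0.00, 0.016, 0.058 and 0.107 SD. The largest is 0.107/0.4 = 27% of the assumed effect. A count limited to days 1-7 gave about 0.00 throughout.

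**3. Acute-care days.** The windows coincide: 0-30 with 0-30, and 0-60 with 0-60. The illustration used section 9.2's control inputs, 22% with any use and a mean of 4.0 days among users. As a check on those inputs, λ/(1 − e^−λ) = 4.0 gives λ = 3.92, excess zeros 1 − 0.22/(1 − e^−3.92) = 0.776 and mean 0.22 × 4.0 = 0.880, against the plan's 0.776 and 0.881. Further inputs were 252 patients (360 × 0.70), an assumed intervention prevalence of 11%, 3 home health days a week while at home, and a true indirect effect of zero. Section 9.2's intervention mean of 1.8 exceeds the control mean and was not used.
- Hospital days displace home health days, nothing else: false indirect effect −0.028 of −0.425 days (about 7%) at 30 days, and −0.016 of −0.428 (about 4%) at 60 days.
- Home health counting also stops at the acute event: −0.250 of −0.425 (about 59%), and −0.280 of −0.428 (about 65%).

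**4. Scale scores at days 30 and 60.** The 30-day count runs up to a day-30 assessment; with the earliest permitted call, day 23, 7/30 = 23% falls after it. The earliest day-60 call is day 53, so the 0-30 day count wholly precedes every day-60 score.

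**The case against.** Section 9.4.1 never pairs a 30- or 60-day count with CTM-15 or PCS, so the defect could be called missing detail in a secondary analysis. It is true that the pairing is a reading of the unrestricted word outcomes, not a stated plan. But the primary outcomes fall naturally under that word, and no count that the plan collects would suit them.

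Four stronger readings are tempting, and the documents do not support them.
- A reader might infer that every indirect effect is uninterpretable. For the scale scores at days 30 and 60, time order is not the main barrier. Mediator-outcome confounding remains, because home health use is not randomised, but that is a different problem.
- A reader might infer that the mediator comes wholly after the day-7 outcomes. The count starts at discharge, so it falls mostly after them, and with a late patient call 43% of the 30-day count does.
- A reader might infer that hospital days mechanically spoil or reverse the acute-care result. Displacement alone had a small effect in the illustration, with the same sign as the total. The outcome also includes ED days, and nothing says that an ED day cannot be a home health day.
- A reader might infer that section 7.2 stops the home health count at hospitalisation. The plan does not say whether chart abstraction stops then, so the 59-65% result is conditional.

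**Conclusion.** The concern holds for CTM-15 and PCS, and for acute-care days and falls. For the first pair, 77% of the 30-day count and 88% of the 60-day count follow a day-7 call. Across the call windows the 30-day share is 43-87% for patients and 70-83% for caregivers. These shares follow from the stated windows alone. For the second pair the overlap is complete and reverse causation cannot be separated. The size of that bias is unknown: small in the illustration from displacement alone, and possibly large if counting stops at withdrawal. The simulated sizes rest on the assumptions given and show direction only.

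The concern does not extend to the four scale outcomes at days 30 and 60 on grounds of time order. It is worth correcting, but it touches a secondary analysis and no main treatment-effect test.

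**What to change.** In section 9.4.1, name each outcome in the mediation analysis and the count paired with it:
- **CTM-15 and PCS:** exclude them. Only if home health visit dates can be abstracted, pair them instead with a count that ends at the call. The plan lists a number of days, not dates, so availability has to be confirmed first.
- **Day-60 scale outcomes:** use the 0-30 day count.
- **Acute-care days and falls:** omit the mediation, or express home health use per day at home and report a non-causal association. State how days in hospital and section 7.2 withdrawals are handled.

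Counting acute-care days only in days 31-60 against home health use in days 1-30 is not a safe repair. Under section 7.2 it would largely restrict the analysis to patients not hospitalised in the first 30 days, and it would replace the stated cumulative endpoint.

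The source of the count also has to be reconciled: section 8.1 describes telephone interviews with home health nurses or therapists, while sections 1.2 and 9.4.4 describe chart abstraction.

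The cost is a few sentences, and an abstraction field if dates are wanted. The downside is fewer outcomes in a secondary analysis.
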